### **3.3 Early Withdrawal of Subjects**

#### **3.3.1 Criteria for removal from study**

Subjects will be removed from the study for safety reasons as described below based on the PHQ-9, pregnancy clinical criteria (history with pregnancy testing as indicated), and PI AE review, or if they withdraw consent.

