If a woman does not meet at least one of the above criteria, then urine will be collected for a pregnancy test, and any subjects found to be pregnant will be informed of their pregnancy test results, and then excluded from the study due to the effects of pregnancy on study outcomes. If the subject has a pregnancy test within 2 weeks before the screening visit, documented in their medical records, these records may be obtained, and after verifying the pregnancy test result in the outside records or the EMR, the pregnancy test result can be accepted in lieu of repeating the test for screening. If the screening visit is conducted remotely, and if a pregnancy test result collected within 2 weeks before the screening visit is not available in the subject's medical record, then the subject will be mailed a urine pregnancy test. Subjects will communicate their urine pregnancy test result to the study team by showing the research coordinator their pregnancy test result as displayed on their urine pregnancy test kit during the (PSH Teams) live

videoconferencing screening visit. Subjects found to be pregnant will be excluded from the study.

Screening Safety Questionnaire: Subjects will be screened for depression and suicidality using the Patient Health Questionnaire-9 (PHQ-9). The PHQ-9 will be self-administered in REDCap and reviewed by the research coordinator for completeness.

If a subject is not comfortable with answering the 9th item of the PHQ-9 at the screening visit, they will be excluded from the study. If a subject refuses to answer the 9th item of the PHQ-9 at any of the subsequent study visits, the subject will be excluded from the study, and the research coordinator will immediately contact one of the below suicidality experts.

PHQ-9 scores will be calculated in REDCap, even if subjects refuse to answer all of the PHQ-9 questions. If a subject's PHQ-9 score at any of the study visits is 10 or greater, they will be advised to see their PCP for further evaluation. The research coordinator will give the subject an Incidental Findings Letter to share with their PCP. This letter will include the subject's PHQ-9 score. These subjects can still continue in the study as long as they meet the other eligibility criteria.

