If a subject scores 1 or greater on the 9th item of PHQ-9, the research coordinator will interview the subject using the modified P4 Screener to assess suicide risk (Dube et al., 2010). If the subject answers 'Somewhat Likely' or 'Very Likely' to the modified P4 Screener question which asks "How likely do you think it is that you will act on these thoughts about hurting yourself or ending your life some time over the next month?", they are considered higher risk and will not be eligible for the study. For these higher risk subjects, the research coordinator will immediately contact one of the following appropriate suicidality experts to initiate a psychiatric consultation:

1. [name] (cell [contact])
2. [name] ([name], cell [contact])
3. Other personnel available for an immediate Psychiatric consult

If on the modified P4 Screener, the subject answers 'Not at all Likely' to "How likely do you think it is that you will act on these thoughts about hurting yourself or ending your life some time over the next month?" and they answer 'No' to "Is there anything that would prevent or keep you from harming yourself?", a follow-up prompt is triggered "What is preventing you from acting on harming yourself?" If the subject provides a response, they are eligible to continue in the study as long as they meet the other eligibility criteria. If the subject cannot/does not provide a response, the subject will be considered higher risk and will be excluded from the study. The research coordinator will immediately contact one of the above suicidality experts.

MINI structured interview: Screening will also include the MINI International Neuropsychiatric Interview (MINI) Version 7.0.2., which is a brief structured interview for the major psychiatric disorders in DSM-V and ICD-10 (Sheehan et al., 1998; Sheehan et al, 1997; Lecrubier et al., 1997; Amorim et al., 1998). The MINI assesses for the 17 most common disorders in mental health that are the most important to identify in clinical and research settings. MINI interviews will be conducted by a trained research coordinator under the supervision of a clinical psychologist ([name]) to screen patients for psychiatric conditions.

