randomized to a later cohort (due to reaching the maximum number of participants permitted in a class, or due to the subject not being reached in time for randomization, or due to the subject requesting to participate in a later cohort when they will be more available). In these scenarios, the screening and baseline visits will need to be repeated if they fall outside of the Study Visit Windows for the new later cohort. In other words, the screening visit will need to be repeated if it is more than 10 weeks and 2 days (72 days) before the new later Orientation session, and the baseline visit will need to be repeated if it is more than 6 weeks before the new later Orientation session. Subjects will need to attend the screening visit and baseline visit within the specified time window in order to be randomized. In these instances, all data from screens and visits that were collected during times when the subject was not randomized will be maintained. However, only the screening and baseline data provided by the subject within the specified time windows will be used in analysis. Data collected from earlier duplicate screens will be maintained and documented securely in REDCap, therefore it is possible that multiple study ID numbers correspond to one randomized subject.

The research coordinator will make 3 attempts to reach a subject for the follow-up phone call within the 2 weeks after Class #4. If a subject misses the follow-up phone call within this specified 2-week time window, the subject will not be withdrawn from the study, and their follow-up phone call data will be considered missing data. If a subject misses the 2-month study visit within the specified time window, the research coordinator will contact them and if the subject confirms that they are willing to come in for the final 6-month study visit, the subject will not be withdrawn from the study and their 2-month study visit data will be considered missing data.

**Lost to Follow-up:** Subjects will be withdrawn from the study and considered lost to follow-up if they cannot be reached after doing the following:

- First, the research coordinator will call and e-mail the subject once a week for 3 weeks.

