- If no response, then the research coordinator will make 3 attempts to call their emergency contact if they provided an emergency contact. Subjects will be asked to provide an emergency contact at the screening visit in case we cannot reach them because they moved, are in a hospital, etc. The emergency contact is usually someone that does not live with them, or at least someone with a different phone number.

This process will be initiated when the subject has not shown up to a study visit. If no response is received from the subject within 60 days of missing the study visit, the subject will be withdrawn from the study and considered lost to follow-up.

**Drop outs/Treatment failures:** Dropouts may occur due to participant choice or physician recommendation for reasons such as adverse effects, poor compliance, etc.

If a subject is randomized but misses Orientation, the instructors may offer the subject an individual Orientation session. If the subject is unable to complete Orientation before Class #2 after being randomized, they will not be permitted to continue in the study.

As soon as a subject is determined to be Lost to Follow-up, Withdrawn or Completed, all data collection will cease after collecting reasons for participant-initiated withdrawal on the Attrition Survey. The date a subject is no longer considered part of the study will be documented in an End of Trial form.

**Attrition Information:** CONSORT guidelines require a reason for dropout for every subject, and whether the reason was due to an adverse event. The research coordinator will collect attrition information for each dropout from the study, and record the dropout date, subjects' responses to Yes/No questions about general reasons for attrition that do not reveal the subjects' group assignment, and whether the dropout is Subject-initiated or Investigator-initiated.

If it is a Subject-initiated dropout or a lost to follow-up, the subject will be e-mailed a link to a REDCap Participant-Completed Attrition Information Survey consisting of one open

ended question to elicit feedback about their experience in the study and learn more about their reasons for not continuing in the study. As subjects' responses could reveal group assignment, the research coordinator and other blinded study team members will be blinded to subjects' responses to this survey in REDCap.

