Investigator-initiated withdrawals: A subject may also be withdrawn from the study and/or intervention by the investigator. In this case, the research coordinator will record the reasons why the investigator withdrew the subject from the study (See DSMP).

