Missed 2-month and 6-month (in-person or remote) study visits: If the subject misses their 2-month or 6-month study visit, and has a lab result (e.g. lab hemoglobin A1c) outside of the study, the lab result (e.g. lab hemoglobin A1c) will be recorded as the study visit lab result (e.g. lab hemoglobin A1c) after verifying the result in outside records or the EMR.

All subjects will be given the same general written guidelines on diet and exercise at the baseline visit, which will consist of two handouts downloaded from the American Diabetes Association Patient Education Library: (1) “Plan Your Portions” Diabetes Placemat and (2) “The Diabetes Advisor - Physical Activity.” All subjects will also be given handouts on Hyperglycemia and Hypoglycemia, as well as Glucometer Best Practices and Blood Glucose Meter Correlation, at the baseline visit. This will be the only information that will be the same across both groups. The MBSR group will not receive any additional health education other than these handouts.

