associations with disease activity, depression, female sex, smoking, and use of corticosteroids or narcotics (N=3173; inflammatory bowel disease) (Ananthakrishnan, 2013), ability to distinguish among those with and without sleep disorders (Buysse, 2010), and prediction (along with negative affect) of global ratings of improvement in back pain (Karp, 2014). The HealthMeasures Scoring Service, powered by Assessment CenterSM, will be used to score the PROMIS Short Form v1.0 Sleep Disturbance 8a. The HealthMeasures Scoring Service is a free, web-based application that scores an Excel file of raw participant responses and returns by email a file with calculated T-scores for all measures. Further details are available at:

[http://www.healthmeasures.net/index.php?option=com\\_content&view=category&layout=blog&id=190&Itemid=1214](http://www.healthmeasures.net/index.php?option=com_content&view=category&layout=blog&id=190&Itemid=1214)

The Patient Health Questionnaire-9 (PHQ-9) will assess safety at each study visit (Kroenke et al., 2001; Van Steenbergen-Weijenburg et al., 2010). This will be self-administered at the study visits as described above in the screening visit. As in the screening visit, if a subject scores 1 or greater on the 9th item of PHQ-9, the research coordinator will interview the subject using the modified P4 Screener to assess suicide risk (Dube et al., 2010).

The Modified Coronavirus Impact Scale will be self-administered to assess how much the Coronavirus pandemic has impacted different aspects of subjects' lives. This survey was modified from the Coronavirus Impact Scale created by Stoddard and Kaufman ([https://www.nlm.nih.gov/dr2/Coronavirus\\_Impact\\_Scale.pdf](https://www.nlm.nih.gov/dr2/Coronavirus_Impact_Scale.pdf)).

Subjects will respond to additional questions in a Participant Questionnaire at the baseline visit (and subsequent study visits). This Participant Questionnaire will assess:

- Adherence to Diabetes Medications by asking subjects to "Rate your ability to take all your diabetes medications as prescribed over the past month" (with six choices: Very poor, poor, fair, good, very good, and excellent) based on a previous study that determined that such a self-report measure most accurately assessed HIV medication adherence (Lu et al., 2008).
- Follow-up Medical History by asking subjects if there have been any changes to their health since the last visit.
- Number of sick days in the past 4 weeks

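### Refusing the suicide item or a P4 question after randomization excludes the subject from the whole study, so month-6 outcome and safety data would probably be lost; the plan is inconsistent on this and should stop the sessions only

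*Combined protocol and SAP*

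**What the plan says.** **Removal triggers.** Section 3.3.1 makes the PHQ-9 a ground for removal, not only for entry: "Subjects will be removed from the study for safety reasons as described below based on the PHQ-9". Section 7.2.2, under the screening safety questionnaire, reaches past screening: a subject who refuses the ninth "item of the PHQ-9 at any of the subsequent study visits, the subject will be excluded from the study". DSMP IV.D repeats this and adds that refusing any modified P4 question, at any study visit, also means exclusion.

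Two further triggers name no visit. A subject who rates acting on suicidal thoughts as somewhat or very likely is called higher risk and not eligible. For the follow-up prompt on what holds the subject back, section 7.2.2 says: "If the subject cannot/does not provide a response, the subject will be considered higher risk and will be excluded from the study". Section 7.2.3 carries the interview to later visits: "As in the screening visit, if a subject scores 1 or greater on the 9th item of PHQ-9, the research coordinator will interview". Section 10.0, which describes monitoring during the study, mentions only referral for suicidal ideation.

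**What removal does.** Section 7.2.2: "As soon as a subject is determined to be Lost to Follow-up, Withdrawn or Completed, all data collection will cease", apart from the Attrition Survey. Section 3.3.2 asks only for the reason for withdrawal. DSMP Appendix A, Table 3 knows three end-of-trial statuses: Completed, Withdrew, Lost to Follow Up.

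**Text pointing the other way.** Section 9.3 and DSMP IV.E state that follow-up of every subject runs to 6 months and that adverse events are followed until they resolve or stabilize. Section 7.2.2 also allows a lesser step: "A subject may also be withdrawn from the study and/or intervention by the investigator".

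**The concern.** The 2-month visit is the only scheduled PHQ-9 after randomization that still has a study visit to come. A subject excluded there is a randomized subject whose primary endpoint lies about four months ahead. If exclusion ends data collection, that endpoint is lost, and so is the later safety course of someone who has just given, or declined to give, information about suicidal thoughts.

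The reason for the loss may relate to treatment: Appendix C2 lists suicidality among previously reported meditation effects. Missing data that arise this way are the kind least safely assumed to be random.

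The rule is also stricter than its neighbours. A subject who misses the entire 2-month visit, PHQ-9 included, but is willing to attend at month 6 stays in: "the subject will not be withdrawn from the study and their 2-month study visit data will be considered missing data". A PHQ-9 total of 10 or more leads to a letter for the primary care provider, not to removal. Section 10.0 reassures subjects that they may leave questions unanswered.

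**Working it through.** **1. Which triggers apply after randomization?**

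| Trigger | Text | Status after randomization |
|---|---|---|
| Refuses PHQ-9 item 9 | 7.2.2, DSMP IV.D: all later study visits | Explicit |
| Refuses a P4 question | DSMP IV.D: any study visit | Explicit |
| Higher-risk P4 answer | 7.2.2, DSMP IV.D: no visit named | Inferred from 3.3.1, 7.2.3 and DSMP IV.D; 10.0 gives referral only |
| No answer to the P4 prompt | 7.2.2, DSMP IV.D: no visit named | Inferred in the same way |

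**2. Does exclusion end data collection?** Excluded is not one of the statuses in the section 7.2.2 stop rule. Section 3.3.1 speaks of removal from the study, and of the three statuses in DSMP Appendix A, Table 3 only Withdrew fits. On that reading the stop rule applies. The 6-month follow-up sentence in 9.3 and DSMP IV.E contradicts it. Loss of the data is therefore the likely reading, not a certain one.

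**3. What would one removal at month 2 cost?** From Table 3 and the table in DSMP IV.E:
- 1 of 2 post-randomization HbA1c values (the primary one)
- 1 of 2 post-randomization PHQ-9s
- 1 of 3 Stress Experience Surveys (Class #4 call, month 2, month 6)
- about 4 months of follow-up

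**4. The plan's sample size.** Inputs from 8.2: difference 0.5, SD 0.9, two-sided alpha 0.05, power 80%, group size 18, ICC 0.08, dropout 15%.
- Design effect: 1 + (18 − 1) × 0.08 = 2.36.
- Two-sample t-test: 52 per arm before inflation.
- 52 × 2.36 / 0.85 = 144.4, rounded up to 145 per arm, 290 in total. The stated figure is reproduced.
- Expected completers: 290 × 0.85 = 246.5. Planned dropouts: 43.5.

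**5. Power if k removals come on top of the 15%.** Effective n per arm = (246.5 − k) / 2 / 2.36; power from the noncentral t. The documents give no rate, so k is an assumption: 1 to 5, with 15 as a stress case.

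| k | Effective n per arm | Power | k as share of planned dropouts |
|---|---|---|---|
| 0 | 52.2 | 80.3% | – |
| 1 | 52.0 | 80.1% | 2.3% |
| 5 | 51.2 | 79.5% | 11.5% |
| 15 | 49.0 | 77.7% | 34.5% |

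If the removals fall within the 15%, power stays at 80.3%. The losses shown are upper bounds, because the mixed model in 8.3 still uses the earlier values. One removal is 1/246.5 = 0.4% of completers.

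**6. How many?** Current suicidality and major psychopathology are excluded at entry (3.2). Section 10.0 puts serious effects of mindfulness programs below 1%, while noting that adequate estimates are lacking: 0.01 × 145 = 1.45, so fewer than 1.5 MBSR subjects. Nothing is given for refusals.

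**7. Bias in the HbA1c contrast.** Assume that removals differ between arms by 1 to 3 percentage points and that the lost month-6 values are 0.5 worse than the model would supply: 0.5 × 0.01 = 0.005 to 0.5 × 0.03 = 0.015, against a target difference of 0.5.

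**The case against.** **The 6-month sentence.** Section 9.3 and DSMP IV.E say that all subjects are followed to 6 months, so a reader could hold that nothing is lost. This stands in part. It rules out the stronger reading that month-6 data are certainly lost. It does not settle the matter, because it contradicts the stop rule in 7.2.2 and does not say that the month-6 HbA1c, PHQ-9 or surveys are still collected after exclusion.

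**Other safeguards.** The footnote to Table 3 allows outside results: "If the subject misses their 2-month or 6-month study visit, and has a lab result (e.g. lab hemoglobin A1c) outside of the study". It is written for missed visits and neither includes nor bars withdrawn subjects. The option to withdraw someone from the intervention alone exists in general but is not applied to the PHQ-9 and P4 rules.

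**A protective rule.** Declining to keep a subject whose suicide risk cannot be assessed is defensible, and refusing a suicide item is a different signal from missing a visit. This supports stopping the sessions and calling the experts. It does not explain why outcome assessment should stop too.

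**Readings to avoid.** A reader might infer that the rule breaks the intention-to-treat statement in 8.3. It does not: data already collected stay in the analysis, and 8.3 does not govern what is collected after removal. A reader might also take post-randomization removal for a higher-risk answer or an unanswered prompt as explicit. Both are inferred.

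**Conclusion.** The point holds as a recommended clarification and a small design change. Exclusion after randomization is explicit for refusing PHQ-9 item 9 or a P4 question. It is a reasonable inference for a higher-risk P4 answer or an unanswered prompt, where section 10.0 points to referral alone. Loss of month-6 data is the natural reading of 3.3.1 with the 7.2.2 stop rule, but 9.3 and DSMP IV.E conflict with it, so the finding is an inconsistency with a probable loss.

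The documents do not support a claim of meaningful harm to the primary analysis. On the assumed 1 to 5 removals, power falls by less than one percentage point, and bias is 0.005 to 0.015 on the HbA1c scale. The gain from the change is outcome and safety follow-up in a few subjects whose removal may relate to treatment.

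For adverse events the conflict is narrower. A refusal is not an adverse event. A higher-risk answer would probably be graded 4 under Appendix C1, subject to the medical assessment required in 9.3. The 7.2.2 stop rule, read literally, would then cut across follow-up to resolution, although it can be read as ending scheduled collection only. The conclusion rests on treating excluded as withdrawn and on small numbers, which the documents suggest but do not state.

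**What to change.** - In 3.3.1, 7.2.2 and DSMP IV.D, state that after randomization the PHQ-9 and P4 triggers end the study sessions only, using the existing option to withdraw a subject from the intervention.
- For subjects who have not withdrawn consent, keep the scheduled month-6 outcome and safety collection, including outside lab HbA1c under the Table 3 footnote.
- In the 7.2.2 stop rule, add an exception for these triggers only. Leave withdrawals for pregnancy or missed Orientation as written: a general rewrite would restart collection for them with no rule for handling the data, and pregnancy is a withdrawal reason because of its effect on the outcomes. State that adverse event follow-up under 9.3 and DSMP IV.E continues.
- State what a higher-risk P4 answer or an unanswered prompt after randomization leads to, so that 3.3.1, 7.2.3, 10.0 and DSMP IV.D agree.
- Keep the immediate contact with the suicidality experts as written.

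Cost: wording in these sections and possibly in the consent form. The month-6 visit is already scheduled at the end of the baseline visit, and the Adverse Events Form already has a code for discontinuing the intervention, so no new form is needed. The downside is a few more contacts with distressed subjects, who may decline.

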aware that the study treatment they are assigned to could have adverse effects, including increased depression, anxiety or panic, re-experiencing of traumatic memories (especially if there is a history of trauma or PTSD), dissociation, executive dysfunction, headaches/body pain and insomnia (Lindahl et al., 2017; Lomas et al., 2014; Cebolla et al., 2014; Brooker et al., 2013; Johnson et al., 2016; Reynolds et al., 2017; Britton et al., 2010). The subject will have the opportunity to interact with one of the study investigators, who reviews the eligibility criteria.

Subjects will be given a copy of the Class Schedule and Homework. This will list the dates and times for all the classes that they could be assigned to and the requirement of at least 25 to 30 minutes of home practice per day for 6 out of 7 days per week. The research coordinator will verify that the subject is available for the intervention sessions with reasonable certainty. If a subject thinks they will miss the Orientation, or if they think they will miss more than 2 classes during the first 8 weeks (including Class #1 to 8 and the Retreat), they will be encouraged to wait for another wave/cohort when they are able to make the time commitment.

After obtaining informed consent, further screening will be completed during the screening visit (See Screening Assessments Form). Subjects will complete the Perceived Stress Scale-10 (PSS-10) questionnaire and need a score  $\geq 12$  to continue in the study. This cutoff is based on normative data from the U.S. population (Cohen & Williamson, 1988). The PSS-10 will be self-administered in REDCap and reviewed by the study coordinator for completeness. REDCap will automatically calculate the PSS-10 score when subjects answer all items on the PSS-10. If any item of the PSS-10 is intentionally skipped, a valid score cannot be calculated to assess inclusion criteria and the subject is ineligible to continue with the screening.

Medical records, when available, will be reviewed to confirm that the subjects have diabetes and are eligible for the study.

**Demographics:** Age (calculated from date of birth), Sex (male or female), Race and Ethnicity will be recorded at screening.

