Subjects' PHQ-9 scores at each of the study visits will be immediately calculated by REDCap, even if subjects refuse to answer all of the PHQ-9 questions. If a subject's PHQ-9 score at any of the study visits is 10 or greater, they will be recommended to see their PCP for further evaluation. The research coordinator will give the subject an Incidental Findings Letter to share with their PCP. This letter will include the subject's PHQ-9 score. These subjects can still continue in the study as long as they meet the other eligibility criteria.

If a subject scores 1 or greater on the 9th item of PHQ-9, a trained research coordinator will interview the subject using the modified P4 Screener to assess suicide risk (Dube et al., 2010). If the subject answers Somewhat Likely or Very Likely to the modified P4 Screener question which asks "How likely do you think it is that you will act on these thoughts about hurting yourself or ending your life some time over the next month?", they are considered higher risk and will not be eligible for the study. For these higher risk subjects, the research coordinator will immediately contact one of the following appropriate suicidality experts, who will immediately evaluate the subject for suicidality and determine if the subject needs to be escorted to the Emergency Department because they have an active suicidal plan in the immediate future:

1. [name] (cell [contact])
2. [name] ([name], cell [contact])
3. Psychiatric consult

If on the modified P4 Screener, the subject answers Not at all Likely to "How likely do you think it is that you will act on these thoughts about hurting yourself or ending your life some time over the next month?" and they answer No to "Is there anything that would prevent or keep you from harming yourself?" the research coordinator will ask "You said 'Not at all Likely' to Q5. What is stopping you from acting on harming yourself?" If the subject provides a response to what is stopping them from acting on harming themselves, they can continue in the study as long as they meet the other eligibility criteria. If the subject cannot provide a response to what is stopping them from acting on harming themselves, the subject will be considered higher risk and excluded from the study, and the research coordinator will immediately contact one of the above suicidality experts.

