**Table 5. Out-of-Range Patient-Reported Safety Assessments in Enrolled Participants**

Pt ID	Visit #	9th item of PHQ-9 (Report if $\geq 1$ )	Full PHQ-9 (Report if $\geq 10$ )	GAD-7 (Report if $\geq 10$ )	Higher Risk for Suicide Based on Modified P4 Screener? (Yes, No, or Not Applicable)

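### Incomplete PHQ-9 forms are scored and compared with 10 without a missing-item rule, and DSMB Table 5 does not show that a form is incomplete

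*Combined protocol and SAP*

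**What the plan says.** Section 7.2.2 (Screening Safety Questionnaire) states: "PHQ-9 scores will be calculated in REDCap, even if subjects refuse to answer all of the PHQ-9 questions". DSMP section IV.D applies the same rule at each study visit: the score "will be immediately calculated by REDCap, even if subjects refuse to answer all of the PHQ-9 questions". Refusing item 9 removes the subject from the study, so the sentence can only sensibly mean that some of items 1 to 8 are blank.

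The score has a consequence: "If a subject's PHQ-9 score at any of the study visits is 10 or greater, they will be advised to see their PCP". The subject also receives an Incidental Findings Letter that contains the score. DSMP Appendix A, Table 5, has a column headed "Full PHQ-9 (Report if" with a cut of 10, and separate columns for item 9 (cut of 1), the GAD-7 (cut of 10) and suicide risk on the modified P4 Screener. No column gives the number of items answered.

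Section 10.0 (Risks of Questionnaires) tells subjects that they may leave any question unanswered. Under DSMP IV.D the coordinator asks about each blank, but enters a response only if the skip was unintended.

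For the PSS-10, section 7.2.2 does give a missing-item rule: "If any item of the PSS-10 is intentionally skipped, a valid score cannot be calculated to assess inclusion criteria".

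**The concern.** The cut of 10 belongs to a nine-item total. A score built from fewer items is not on that scale unless the plan says how it was put there. No formula, minimum item count, pro-rating or incomplete marker appears for the PHQ-9. A partial score below 10 is therefore handled as a negative screen when it may be undetermined.

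The PHQ-9 is the plan's depression screen at screening, baseline, 2 months and 6 months, and section 10.0 names increased depression as a reported effect of meditation. The MINI is done only at screening. A subject recorded below 10 because of refused items gets neither the advice nor the letter. The DSMB cannot tell that form from a complete one with the same score. Even when a subject is flagged, the letter may give an understated score with no note that items were missing.

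**Working it through.** The plan gives no figure on this point, so there is none to reproduce. The question is how far a recorded score can fall below the total that a complete form would have given.

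**Inputs**
- Nine items and a cut of 10: section 7.2.2 and DSMP IV.D.
- Item 9 always present in a continuing subject, so k refusals fall among items 1 to 8: section 7.2.2.
- Each item scored 0 to 3: an assumption, since the documents do not give the item range.
- Scoring method: not stated. Two variants are compared, a plain sum of the answered items and a sum pro-rated by 9/(9 − k).

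**Plain sum.** The recorded score is the complete total minus the refused items' values, each 0 to 3. The highest complete total that can be recorded as 9 or less is 9 + 3k.

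**Pro-rated sum.** The score reaches 10 when the answered sum is at least 10(9 − k)/9, rounded up. This gives 9, 8 and 7 for k = 1, 2 and 3. The highest complete total still scored below 10 is one less than that sum, plus 3k.

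| Refused items (k) | Plain sum: highest total missed | Pro-rated: answered sum that flags | Pro-rated: highest total missed |
|---|---|---|---|
| 1 | 9 + 3 = 12 | 9 | 8 + 3 = 11 |
| 2 | 9 + 6 = 15 | 8 | 7 + 6 = 13 |
| 3 | 9 + 9 = 18 | 7 | 6 + 9 = 15 |

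The plain-sum limits also hold when item 9 is 0, the case that matters for Table 5. The other answered items, 8 − k of them, can sum to at most 21, 18 or 15, so a recorded 9 is always attainable.

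**A milder case.** If symptoms are spread evenly over the items, a plain sum records T(9 − k)/9 for a complete total T. Reaching 10 then needs T = 90/(9 − k), which is 11.25, 12.9 and 15.0. The totals missed are 10–11, 10–12 and 10–14.

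**Illustration.** Weighting all response patterns equally, a complete total of 10 drops below 10 in 63%, 88% and 97% of patterns with one, two and three refusals under a plain sum. Under pro-rating the figures are 34%, 42% and 45%. These are shares of patterns, not of patients.

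**What follows.** Under a plain sum, a partial score of 10 or more is a sound flag, because the answered sum is a lower bound on the complete total. Only partial sums below 10 are undetermined. Pro-rating reduces the missed cases but does not remove them, so incomplete forms need marking under either method.

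**The case against.** A reader might infer that each refused item counts as zero. The documents do not say so: REDCap may already pro-rate. Even under a plain sum, the score is too low only if the refused item would have been above zero.

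A reader might also infer that an under-scored subject drops out of the DSMB table. That is not automatic. Table 5 still lists anyone with item 9 of at least 1, or with a GAD-7 of at least 10 at the visits where it is given (baseline, 2 months and 6 months, but not screening). The Stress Experience Survey asks about depression too. Under DSMP E.3.1, any item more frequent than at baseline or the previous visit is recorded as an adverse event, and adverse events are reported in Table 6. Worsening can therefore reach the DSMB without a PHQ-9 total. The suicidality steps depend on item 9, not on the total.

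The contrast with the PSS-10 is weaker than it looks. The PSS-10 total decides eligibility, whereas a PHQ-9 score of 10 or more does not exclude anyone. Scoring partial forms for a safety flag is reasonable, because it catches subjects who reach 10 on the items they answered.

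All of this stands and narrows the point, but none of it supplies the missing rule. A subject with item 9 at 0, a GAD-7 below 10 and a partial PHQ-9 below 10 gets no advice, no letter and no Table 5 entry. The Stress Experience Survey detects an increase, not a steady high level.

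**Conclusion.** The point holds as a gap in specification. The plan scores incomplete forms and applies the cut of 10 without saying how, and Table 5 does not separate an incomplete form below 10 from a complete negative one. If answered items are summed and scored 0 to 3, complete totals up to 12, 15 or 18 can be recorded as 9 or less with one, two or three refusals, and the error runs only towards missed cases. If REDCap pro-rates, the limits are 11, 13 and 15.

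The documents do not support saying that scores will be too low or that the DSMB will lose these subjects: the scoring method is unstated and other routes into the reports exist. The number affected cannot be estimated, because no refusal rate is given and only deliberate refusals of items 1 to 8 remain after the coordinator's check. The primary HbA1c analysis is not affected. The gap is still worth closing, because it sits in a safety screen and the repair is small.

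**What to change.** In section 7.2.2 and DSMP IV.D, replace the sentence on incomplete forms with a scoring rule in three steps:

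1. Any answered-item sum of 10 or more counts as 10 or more, however many items are missing.
2. Otherwise, with one or two of items 1 to 8 missing, the total is pro-rated (sum ÷ items answered × 9) before comparison with 10.
3. With more items missing and a sum below 10, the form is recorded as indeterminate, not as below threshold.

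Step 1 has to come first. A rule that made heavily incomplete forms unscorable would drop subjects whom the current text flags, such as one whose six answered items sum to 12.

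Record the number of items answered. In Table 5, list every incomplete form with a total below 10, marked as incomplete, since pro-rating still leaves some cases missed. The threshold of 10 and the actions attached to it do not change.

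The cost is a REDCap scoring field, a count of items answered and one table column. The downside is that a few extra subjects are flagged or listed.
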